6.5 Stopping Rules

If patients exhibit respiratory distress or serious allergic reaction following 5-ALA administration, their participation in the study will cease

Stopping rules for trial enrollment have been incorporated into the protocol based on liver function tests (LFTs). The extensive European experience with Gleolan® and fluorescence- guided tumor resection has shown that patients very commonly have a transient increase in their liver enzymes (>=1/10). Peak values occur between 7 and 14 days after administration. However, LFT increases can occur up to 6 weeks after administration. The liver toxicity data available from the Phase III European trial (Stummer 2006) has shown that after 6 weeks, the incidence of Grade 3 and Grade 4 events (>5-10x or >10x upper limit of normal) occur in less than 6% of patients for ALT/GPT, AST/GOT, and Gamma-GT (GGT) liver testing. Approximately 10% had Grade 3 or 4 elevations in GGT at 7 days; 5% had Grade 3 or 4 elevations in GGT at 6 weeks, and 1% had persistent ALT or AST elevations at 6 weeks. LFTs returned to normal in all patients. In both groups of patients from the European phase III trial, (Gleolan® and placebo control), 1 patient developed a hepatic serious adverse event (SAE). The Gleolan® patient developed cholelithiasis.

Patients will be continuously monitored for sustained Grade 3 or 4 elevations in their LFTs at six weeks following Gleolan® administration. A comprehensive metabolic serum panel, including albumin, alkaline phosphatase, total bilirubin, bicarbonate, BUN, calcium, chloride, creatinine, glucose, potassium, total protein, SGOT[AST], SGPT[ALT], sodium, gamma glutamyltranspeptidase (GGT), will be obtained prior to surgery, within 48 hours of surgery, 2 weeks, and 6 weeks after surgery. These tests will only be repeated after 6 weeks if SGOT[AST], SGPT[ALT], and gamma glutamyltranspeptidase (GGT) remain elevated after 5-ALA dosing.

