We will continuously monitor the rate of sustained Grade 3 or 4 elevations in LFTs at 6 weeks following Gleolan® administration and accrual will be halted if there is sufficient evidence that the sustained Grade 3 or 4 LFT elevation rate exceeds the acceptable rate of 5% by more than 5% (unacceptable rate 10%). If the cumulative number of patients that experience grade 3 or 4 elevations in the LFTs at 6 weeks from drug administration is greater than the associated boundary value $b_{\mbox{\tiny K}}$ listed in the table below, among the k patients enrolled in the trial, enrollment in the trial will be halted for safety considerations prompting IRB notification and a DSMB meeting will be requested.

# of accrued	2-9	10-20	21-23
subjects, k			
Boundary, b _k	1	2	3

The following table shows the probability of early stopping if the true rates of sustained grade 3 or 4 elevations in the LFTs are at or lower than 10%. For safety of the participants, we would like to have a low probability of early stopping if the sustained LFT rates are low, but high probability of early stopping if the sustained LFT rate is high.

Probability of early stop based on true grade 3 or 4 LFT rate					
True SAE rate	5%	6.2%	7.5%	8.8%	10%
Probability of early stop	0.15	0.21	0.28	0.36	0.44

This stopping rule was computed using the toxbdry function in R and calculations of this function are based on methods described in Chapter 12 of Jennison and Turnbull³⁹ and in the illustrative paper by Ivanova, Qaquish and Schell⁴⁰.

toxbdry(0.05,0.10,c(1:23),cP0=0.15,cP1=0.30,ngrid=5)

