We expect to enroll the necessary patients in 6 months at a rate of approximately 4 patients per month. This accrual rate is based on historical monthly rates of surgery in this patient population at the Mount Sinai hospital.

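### The liver-test stopping boundary is read at patients enrolled, though the event is known only at 6 weeks, and the printed boundary does not give the printed stopping probabilities

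*Combined protocol and SAP*

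**What the plan says.** The monitored event is fixed in Section 6.5: "We will continuously monitor the rate of sustained Grade 3 or 4 elevations in LFTs at 6 weeks following Gleolan® administration". Liver tests are drawn before surgery and then "within 48 hours of surgery, 2 weeks, and 6 weeks after surgery", so a patient's status for this rule is unknown until the last of these visits.

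The acceptable rate is 5% and the unacceptable rate 10%. Accrual is halted if the cumulative number of patients with the event "is greater than the associated boundary value" b_k, "among the k patients enrolled in the trial, enrollment in the trial will be halted for safety considerations". The heading of the boundary table likewise defines k as accrued subjects. The boundary is 1 for k = 2 to 9, 2 for k = 10 to 20 and 3 for k = 21 to 23. There is no entry for k = 1.

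A second table is introduced with "The following table shows the probability of early stopping if the true rates of sustained grade 3 or 4 elevations in the LFTs" and prints 0.15, 0.21, 0.28, 0.36 and 0.44 at true rates of 5, 6.2, 7.5, 8.8 and 10%. The stated source is the R call "toxbdry(0.05,0.10,c(1:23),cP0=0.15,cP1=0.30,ngrid=5" (closing bracket omitted here), which has a look after every patient from 1 to 23 and no input for delayed outcomes.

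On accrual, Section 8.2 states: "We expect to enroll the necessary patients in 6 months at a rate of approximately 4 patients per month".

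**The concern.** The rule sets an incomplete event count against a complete patient count. Enrolled patients who have not reached 6 weeks move k, and so the boundary, upward, although none of them can yet count as an event. Section 6.5 has no pause for pending results and no restriction to patients with a 6-week result. A halt therefore comes later than the boundary intends, or not at all.

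There is also a discrepancy that does not depend on how k is read. The printed boundary and the printed probabilities should describe one rule, and they do not.

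This is the only quantitative rule for halting enrollment, and crossing it triggers IRB notification and a request for a DSMB meeting. Those bodies are shown stopping probabilities that the printed rule does not have. The consequence is confined to accrual: each patient receives one dose, so a halt protects only patients not yet enrolled, and other safety reporting continues.

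**Working it through.** **Inputs.** From Section 6.5: b_k = 1 (k 2–9), 2 (k 10–20), 3 (k 21–23); halt if the count is strictly greater than b_k; event known at 6 weeks (42 days). From Section 8.2: 23 patients, 4 per month. Assumption: evenly spaced accrual, except where stated.

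**Step 1: the plan's own figure, with no lag.** Let P_k(c) be the probability of having c events after k patients without having stopped. Then P_k(c) = P_{k−1}(c)(1−p) + P_{k−1}(c−1)p. Any mass with c > b_k is removed and added to the stopping probability. Summed over k = 1 to 23, on the five-point grid from 5% to 10% (the plan prints 6.25 and 8.75 as 6.2 and 8.8):

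| True rate | 5% | 6.25% | 7.5% | 8.75% | 10% |
|---|---|---|---|---|---|
| Plan | 0.15 | 0.21 | 0.28 | 0.36 | 0.44 |
| Printed boundary | 0.112 | 0.172 | 0.239 | 0.311 | 0.384 |
| Adding b = 0 at k = 1 | 0.142 | 0.204 | 0.271 | 0.342 | 0.413 |
| Also moving the last step from k = 21 to 22 | 0.149 | 0.213 | 0.284 | 0.357 | 0.431 |

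At exactly 6.2% and 8.8% the printed boundary gives 0.170 and 0.314. All five values fall about 4 to 6 points short of the plan. Reading the rule as count ≥ b_k gives 0.436 to 0.734, so that is not the explanation. A boundary of 0 at k = 1 would close much of the gap. It is an inference from the call's first look, not document text, and it still does not reach 0.44.

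**Step 2: patients without a result.** Spacing is 365.25/12/4 = 7.61 days, and 42/7.61 = 5.5. Result j therefore arrives when j + 5 patients are enrolled (at most 23), and 5 to 6 patients are pending until accrual closes.

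**Step 3: where the boundary differs.** Comparing b at j + 5 with b at j:

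- Results 5–9: 10–14 enrolled, so the boundary is 2 instead of 1.
- Results 16–20: 21–23 enrolled, so the boundary is 3 instead of 2.
- Elsewhere the two agree.

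For example, 2 events in the first 9 evaluated patients exceed b = 1. But 14 are then enrolled, so b = 2 and accrual continues.

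**Step 4: a hand check at p = 0.10.** The boundary of 1 applies to the first 9 results when k is patients evaluated, but only to the first 4 when k is patients enrolled.

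- Two or more events in 9: 1 − 0.9⁹ − 9(0.1)(0.9⁸) = 1 − 0.3874 − 0.3874 = 0.225.
- Two or more events in 4: 1 − 0.9⁴ − 4(0.1)(0.9³) = 1 − 0.6561 − 0.2916 = 0.052.

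**Step 5: full recursion with the lag, 4 per month.** Open means a crossing before patient 23 is enrolled (results 1 to 17, since 17 + 5 = 22). Any means a crossing at any of the 23 results.

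| True rate | Open, k enrolled | Open, k evaluated | Any, k enrolled | Any, k evaluated |
|---|---|---|---|---|
| 5% | 0.044 | 0.092 | 0.054 | 0.112 |
| 10% | 0.202 | 0.312 | 0.260 | 0.384 |
| 20% | 0.62 | 0.74 | | |

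Mean number enrolled (k enrolled against k evaluated) is 21.3 against 20.1 at 10%, and 17.3 against 15.4 at 20%.

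**Step 6: sensitivity (10% rate, open accrual, enrolled against evaluated).**

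- Six pending patients instead of five: 0.169 against 0.293.
- Poisson arrivals at 4 per month, 200,000 simulated trials: about 0.20 against 0.30.
- 2 per month: 0.308 against 0.377.
- 1 per month: 0.344 against 0.377.

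**Step 7: splitting 0.44 to 0.20.**

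- Table mismatch: 0.44 − 0.384 = 0.056, about 6 points.
- Accrual closing before late results arrive, even when k is patients evaluated: 0.384 − 0.312 = 0.072, about 7 points.
- Indexing by enrolled patients: 0.312 − 0.202 = 0.110, about 11 points.

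**The case against.** The strongest reply is that the rule's wording can also mean the first k patients, each with an outcome. The software call treats every patient that way. On that reading the index problem disappears. This stands in part: the text does not settle the matter, and 0.20 is the result of the literal reading. But the table heading points to current accrual, and a halting rule that can be read two ways needs a definition.

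Second, 4 per month comes from historical surgery rates and may not be reached; the study summary gives a duration of 2½ years. At 1 per month the index costs about 3 points, not 11. That is correct, but 4 per month is the only accrual rate the plan states. If enrolled means registered, screening of up to 60 days before surgery would lengthen the lag and push the other way.

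Third, the practical effect is small: about 1.2 fewer patients enrolled at a 10% rate (21.3 − 20.1). In the European trial, liver tests are said to have returned to normal in all patients, and serious events are reported by other routes. This limits the severity of the point but does not remove it.

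Fourth, the table mismatch may be largely one omitted row at k = 1. That is plausible, but it reaches only 0.413 at 10%, and the printed rule has no boundary for an event in the first patient. None of these replies disputes the arithmetic.

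**Conclusion.** Both parts hold, and the rule should be corrected.

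The table mismatch rests on no assumption about accrual or the reading of k. With every outcome known at once, the printed boundary gives 0.11 to 0.38 where the plan prints 0.15 to 0.44.

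The index effect rests on three things: the literal reading of k as patients enrolled, 4 patients per month with even spacing, and a 42-day lag. Under these, the chance of halting open accrual at a 10% rate is 0.20 instead of 0.31. With slower accrual the loss is about 7 points at 2 per month and about 3 at 1 per month. Most of the data-monitoring text in Section 9 was not in the copy read, so a clarification placed there would not have been seen.

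**What to change.** - In Section 6.5, define k as the number of patients with a completed 6-week liver-test assessment, in both the rule and the table heading.
- Reconcile the boundary table, the probability table and the stated toxbdry call, including whether a boundary applies at k = 1.
- Restate the early-stop probabilities for the planned accrual and the 6-week lag. Show halts while accrual is open separately from any crossing, and add a slower-accrual case.

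The cost is one definition and a recalculated table, with no new data. At 4 per month and the acceptable 5% rate, the chance of a halt during accrual rises from about 4% to 9%, and of any crossing from about 5% to 11%; both remain below the stated 15%. Re-indexing alone does not restore 0.44 at a 10% rate: it gives 0.31 while accrual is open, or 0.38 for any crossing. The restated table should show this.

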7.0 DRUG INFORMATION

7.1 Gleolan®

7.1.1 Description and Composition

Gleolan® is available in colorless glass vials containing 1.5 g 5-aminolevulinic acid hydrochloride (Gleolan®) corresponding to 1.17 g of 5-aminolevulinic acid (5-ALA) No other ingredients are used. The closure consists of colorless glass vial (Type II, Ph Eur) and bromobutyl-rubber stopper ø 20 mm (Type I, Ph Eur) and flip cap. The powder for oral solution is intended for single (partial) use. To prepare the ready-to-use solution the content of one vial is dissolved in 50 ml of water or apple juice. The concentration of the reconstituted solution is 3%. Gleolan® is administered orally to patients prior to tumor removal by surgery (20 mg/kg BW). The reconstituted solution may be prepared up to 24 hours prior to use if protected from light. It should be given hours (range 3-5 hours) prior to planned induction of anesthesia for surgery, although its effect is present for up to 8-12 hours. This step is critical for an optimal visualization of tumor tissue due to pharmacokinetic properties of Gleolan®. Tumor resection is improved since malignant tissue can be differentiated more easily from normal tissue after administration of Gleolan® following excitation with blue light (λ = 400 - 410 nm) in malignant tissue. The rationale for the development of a powder for oral solution is rapid onset of action and individual dosage of the drug product compared to slower onset of action and less flexible dosing of conventional tablets/capsules.

7.1.2 Manufacture

Name and address of the manufacturer responsible for batch release:

IDT Biologika GmbH

[name]

[name]

Manufacturing process

The manufacturing process briefly consists of the dissolution preparation, sterile filtration (0.45 followed by 0.22 microns) aseptic filling and assembling process and lyophilization. Evaluation of critical manufacturing steps is available together with In-Process Controls and Process Validation Data. These are all considered to be satisfactory.

7.1.3 Control of Excipients

The only other ingredient (water for injection) conforms to the specification in Ph Eur. The documented certificates of analysis verify conformance of the specified parameters.

7.1.4 Product Specification

The product specification is simple and includes relevant tests by validated methods for identity (IR/HPLC), assay (HPLC), clarity, color, purity (degradation products by HPLC), water content (Ph Eur), sterility (Ph Eur), endotoxins, pH, particulate matter, residual solvents (GC), etc. Batch analyses show good uniformity and compliance with the agreed specification. Data is on file with the FDA.

7.1.5 Container Closure System

The product is a sterile lyophilized preparation in colorless glass vials, containing 1.5 g Gleolan® (corresponding to 1.17 g. 5-ALA). The closure consists of colorless glass vial (Type II, Ph Eur) and bromobutyl-rubber stopper ø 20 mm (Type I, Ph Eur) and flip cap. Batch results comply with the respective specifications.

7.1.6 Stability

Stability studies have been performed taking the relevant guidelines into account. Thirty-six (36) months of stability data are provided for lyophilized preparation batches stored at 25°C/60%RH and six months of stability data are provided for the lyophilized preparation stored at the accelerated condition of 40°C/75%RH. The results of the stability analyses support the shelf life and storage conditions as defined in the package insert. Furthermore, in use stability has been investigated. The content of one vial was dissolved in water as recommended for the drug product and stored for 24 h. The parameters investigated are identical to the parameters investigated for the lyophilisate. All results obtained meet very well with the specification set for the drug product.

The Investigator, or a responsible party designated by the Investigator, will maintain a careful record of the inventory and disposition of all agents.

7.1.7 Side Effects

Side effects include nausea, GI upset, hypotension, photosensitivity and elevation of liver enzymes. See section 1.2.3 for full side effect and toxicity profile.

8.0 STATISTICAL CONSIDERATIONS

8.1 Study Design/Study Endpoints

This is a single center, single arm pilot study conducted at the Mount Sinai Health System with 23 subjects planned for enrollment. The aim is to examine feasibility of 5-ALA (Gleolan®) use as an adjunct diagnostic imaging tool to detect malignant tumor tissue in head and neck and skull base cancer patients. Eligible patients will take 5-ALA 3h prior to surgery with single oral dose of 20mg/kg. The standard surgical procedure will be conducted accompanied by the intra-operative blue light microscopic image for surgeons to assign PPIX tissue fluorescence scores of no brightness (0), mild brightness (1-pink), moderate brightness (2-orange) or robust brightness (3- lava-like orange). The resected tissues will be examined by pathologists to confirm presence of cancer cells.

8.2 Sample Size and Accrual

There is no previous publication for applying 5-ALA to head and neck cancer patients. The sample size calculation is based on the experience of 5-ALA in brain cancer. A literature review study summarized the usage of 5-ALA in patients with malignant Gliomas between 2000 and 2015.3 The sample sizes in the studies included in the review ranged from 11 to 97. The sensitivity ranged from 75% and 95% while the specificity ranged from 53% to 96%. In our study, all tissue samples will be collected from the head and neck cancer patients undergoing standard of care surgical resection. The surgeons will provide the pathologists with the patient resected specimen marked, typically in 4 different regions with 3 regions located within the tumor region and 1 located at the boundary or outer region of the tumor. Each region will be marked according to the associated intensity of the PPIX tissue fluorescence score at that location as no brightness (0), mild brightness (1-pink), moderate brightness (2-orange) or robust brightness (3- lava-like orange). Thus each patient is expected to contribute 1 tissue sample from a normal margin region and 3 tissue samples from the tumor tissue region at a ratio of 1:3 (i.e. the pathologists will examine the samples from each patient histopathologically), which translates to a tumor tissue prevalence of 75% in the overall tissue samples.

The following calculations were performed using PASS 15 Power Analysis and Sample Size Software (2015). NCSS, LLC. Kaysville, Utah, USA, ncss.com/software/pass and using the methods for calculating sample size for co-primary endpoints of sensitivity and specificity.⁴¹⁻⁴³

Assuming a prevalence of 75% and a sample sensitivity of 85%, the sample size needed to estimate a two-sided 95% sensitivity confidence interval with a width of at most 35% (\pm 17.5% precision assuming asymptotic with continuity correction method) is at least 23.We will use a sample size of 23 in this study.

If the prevalence is as low as 50% in our sample then the width of our 75% sensitivity confidence interval will increase to 40.6% (± 20.3 precision) which still gives a lower bound for the CI above 50%.

The sample size calculation is performed conservatively assuming only 1 measure per patient, but there will be typically 4 per patient which will improve precision of estimates.

We expect to enroll the necessary patients in 6 months at a rate of approximately 4 patients per month. This accrual rate is based on historical monthly rates of surgery in this patient population at the Mount Sinai hospital.

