Photographs will be taken during the 'blue light' imaging to provide identification of optical fluorescent tumor. Images will be taken before, during and after resection to capture tumor fluorescence. All tumor specimens will be sent to pathology for frozen examination as per institutional standard of care. Any tissue specimens from the fluorescent areas will be photographed and sent for permanent histopathologic examination and molecular genetic analysis to confirm the presence of malignant tumor. The intraoperative pictures of the resection cavity in the 'blue light' mode will be analyzed to provide confirmation of tissue/tumor fluorescence associated with tumor resection. The surgeon will document whether visualization of fluorescence was present with each of the labeled tissue specimens. The remainder of the resection will be performed with the ability to switch between white light and blue light as chose by the surgeon. If no fluorescence is observed in the resection site it will be noted, but will otherwise undergo identical tumor resection, photography and histopathologic examination.

Pathologic confirmation of tumor type will be made by a pathologist who will not be informed of the fluorescence status of the tissue samples. Histopathology will characterize the resected tissue as

- (1) Diagnostic tissue or not
- (2) Presence of malignant tumor cells
- (3) Pathologic grading and tumor type

Genetic testing will be performed in accordance with standard of care at the testing institution for the tumor specimens.

4.5 **Duration of Therapy**

One-time, single dose administration of oral Gleolan®(5-ALA) (20mg/kg) is planned 3-5h prior to induction of anesthesia. However, surgery can be initiated up to 8 hours after dosing. In the event of allergic reaction, other severe adverse effect, or changes in the patient's condition prior to surgery rendering the patient unacceptable for further treatment in the judgement of the investigator, or patient decides to withdraw from the study, the therapy protocol will be ended and fluorescent-guided surgery will not proceed.

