8.3 Data Analyses Plans

The characteristics of participants and information collected before 5-ALA is administered will be summarized using standard statistics, such as mean, SD, median, 1st and 3rd quartiles for continuous variables, and count, percentage for categorical variables.

Analysis of the primary endpoint

To assess the feasibility of using 5-ALA as an adjunct diagnostic imaging tool to detect malignant tumor tissue, the point estimate of sensitivity will be computed according to the following definition:

Sensitivity: proportion of tumor tissues that tested positive on 5-ALA induced fluorescence.

The definition of a positive test is the fluorescence score equal to or greater than 1 while a negative test is considered a score of 0. For the assessment of sensitivity and

specificity, histological diagnoses of any upper aerodigestive head and neck cancer in addition to squamous cell carcinoma, carcinoma in situ, and severe and moderate dysplasia were classified as malignant, whereas light dysplasia and normal tissue will be classified as benign by pathologists. The analysis population includes all patients who sign the inform consent regardless of taking 5-ALA or not. Each patient is expected to contribute multiple samples and the pathologists will determine presence of malignancy in each sample. A contiguous table (fluorescence scores vs. pathological results) that presents the frequency and percentage of each cell will be prepared. A generalized estimating equation (GEE) model accounting for repeated measure within each patient will be used to estimate the sensitivity and specificity.⁴⁴⁻⁴⁵ For sensitivity and specificity, the dependent variable is the PPIX fluorescence test result (positive vs. negative) and the independent variable is presence of tumor cells (tumor vs. normal).

Analysis of the secondary endpoints

To further determine the diagnostic performance of 5-ALA for detecting of malignant tumor tissue, specificity, PPV and NPV will be computed. Specificity will be computed according to the following definition:

Specificity: proportion of normal tissues that tested negative on 5-ALA induced fluorescence.

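### Section 8.2 sends specimens to pathology marked with the fluorescence score, against the masking promised in Section 4.4, which would bias sensitivity and specificity towards agreement

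*Combined protocol and SAP*

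**What the plan says.** Section 4.4 (Other Modalities or Procedures) commits to a masked reference reading: "Pathologic confirmation of tumor type will be made by a pathologist who will not be informed of the fluorescence status of the tissue samples". The list that follows it of what histopathology will characterize includes whether malignant cells are present.

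Section 8.2 (Sample Size and Accrual) describes what reaches the pathologist: "The surgeons will provide the pathologists with the patient resected specimen marked, typically in 4 different regions". It then says what the marks convey: "Each region will be marked according to the associated intensity of the PPIX tissue fluorescence score at that location", on the four-level scale from 0 to 3.

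Section 8.3 (Data Analyses Plans) gives both sides of the accuracy comparison. For the index test, "The definition of a positive test is the fluorescence score equal to or greater than 1", with 0 negative. For the reference standard, "the pathologists will determine presence of malignancy in each sample". Moderate dysplasia and worse count as malignant; light dysplasia and normal tissue count as benign.

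**The concern.** The mark described in Section 8.2 carries the index test result itself, since 0 against 1 or more is the test's positive/negative cut. A pathologist who receives the specimen in that form can see, for each region, the result that the histology is meant to judge.

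Many reads are clear-cut and will not move. The exposed ones are judgement calls: moderate against light dysplasia, which is where Section 8.3 draws the malignant/benign line, and scattered tumor cells in the sample from the tumor's boundary or outer region. These are also the calls that populate the discordant cells of the 2x2 table.

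At stake are the primary endpoint and the secondary accuracy measures, all of which compare score with histology. The planned GEE model handles correlation within patients; it does nothing about a reference standard that has been influenced by the test. Once the reads are made, only a masked re-read could repair them.

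**Working it through.** **Step 1. Set the passages side by side.**

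- Reader of the reference standard: kept unaware of fluorescence status (4.4).
- Material given to that reader: the specimen, already marked by the surgeon (8.2).
- Content of the marks: the score at each location (8.2).
- Meaning of the score: 0 is a negative test, 1 to 3 a positive test (2.3 and 8.3).
- Use of the reading: it decides tumor or normal for each sample (8.3).

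Sections 4.4 and 8.2 are compatible only if the mark cannot be read as a score. I found no neutral code, no separately held key and no step that removes the marks before reading.

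**Step 2. Reproduce the planned sample size.** The inputs from 8.2 are sensitivity 0.85, prevalence 0.75, a two-sided 95% interval of width at most 0.35, and the asymptotic method with continuity correction. With n tumor samples the half-width is 1.96 × √(0.85 × 0.15 / n) + 1/(2n).

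- At n = 17 this is 0.1697 + 0.0294 = 0.1991.
- The lower limit is 0.651 and the upper limit is cut at 1, so the width is 0.349.
- 17 / 0.75 = 22.7, rounded up to 23.

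The plan's 23 is reproduced. This point does not dispute it and the remedy does not change it.

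**Step 3. Illustrate the bias.** Section 8.2 expects three tumor samples and one normal sample per patient, so 23 patients give 69 and 23. True sensitivity is taken as 85% (8.2). True specificity of 75% is my assumption, inside the 53% to 96% that 8.2 cites from glioma. A fraction f of discordant samples is read in line with the visible mark; f is also an assumption.

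True expected cells:

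- TP = 69 × 0.85 = 58.65; FN = 10.35
- TN = 23 × 0.75 = 17.25; FP = 5.75

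A tumor sample scored 0 that is read as benign moves from FN to TN. A normal sample scored 1 or more that is read as malignant moves from FP to TP. Hence:

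- reported sensitivity = (TP + f·FP) / (TP + f·FP + (1 − f)·FN)
- reported specificity = (TN + f·FN) / (TN + f·FN + (1 − f)·FP)

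At f = 20%, sensitivity = 59.80 / (59.80 + 8.28) = 87.8% and specificity = 19.32 / (19.32 + 4.60) = 80.8%. The numbers of positive and negative tests stay at 64.40 and 27.60, so PPV goes from 58.65/64.40 = 91.1% to 59.80/64.40 = 92.9%, and NPV from 17.25/27.60 = 62.5% to 19.32/27.60 = 70.0%.

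| True sensitivity / specificity | f = 10% | f = 20% |
|---|---|---|
| 85% / 75% | 86.4% / 77.9% | 87.8% / 80.8% |
| 70% / 75% | 72.4% / 78.9% | 74.9% / 82.3% |

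The second row shows a test that performs worse than planned; 70% lies below the 75% to 95% range cited in 8.2.

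**Step 4. Vary the truth over the ranges in 8.2.** With sensitivity from 75% to 95%, specificity from 53% to 96% and f = 20%, sensitivity rises by about 1 to 5 points and specificity by about 1 to 11 points. In these formulas both must rise whenever f is above 0 and there are discordant samples of both kinds, because each numerator grows while the matching error count shrinks.

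**The case against.** The strongest reply is that Section 4.4 is the operative procedure and is unambiguous, whereas Section 8.2 only explains where the 75% prevalence comes from. Marking by score need not mean a legible score: a suture, ink or code whose meaning the surgeon keeps would satisfy both sections. Section 4.4 also has the surgeon document fluorescence for each labeled specimen, which suggests a record held elsewhere. This stands to the extent that actual unmasking is not certain. It does not reconcile the text: Section 4.4 does not say the labels are neutral, Section 8.2 is the only place that says what the marks encode, and staff who follow it literally would unmask the reader while complying with the protocol.

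Second, the figures are illustrative. Neither f nor the 75% specificity has a source in the plan. A uniform f may overstate the effect on sensitivity, because three of four regions lie within the tumor, where borderline reads should be fewer. In the 85% case the shift in sensitivity is 1.4 to 2.8 points, against a stated precision of ±17.5 points and with no success threshold to cross. All of this is fair. It limits how much weight the size can bear, not the direction of the bias or the fact that a larger sample would leave it in place.

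Third, the masking in Section 4.4 arguably already covers the malignant/benign call, given the list after it. That is a reasonable reading, but the sentence itself names only tumor type, so a clarification is worthwhile.

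Finally, neutral codes would not hide everything, since a specimen's location may still hint at its score. That is true, but it leaves far less information with the reader than the score itself.

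**Conclusion.** The concern holds. As written, Sections 4.4 and 8.2 contradict each other on whether the reader of the reference standard can know the index result, and following Section 8.2 breaks a masking commitment that the plan itself makes. The conflict is certain on the natural reading of the text. The bias depends on the marks being legible to pathology and influencing some reads; if they do, the expected direction is upward for sensitivity, specificity, PPV and NPV. Its size is unknown. The illustration suggests one to a few points for sensitivity and more for specificity, subject to the assumed f and true accuracy. It should be corrected before specimens are read, because the analysis cannot undo it afterwards.

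**What to change.** 1. In Section 8.2, replace marking by score with neutral region codes (for example A to D), assigned in an order unrelated to the score.
2. Record the code-to-score key on the intraoperative case report form. The surgeon already assigns scores (Section 5.2.2) and documents fluorescence per labeled specimen (Section 4.4), so the score need not travel with the tissue.
3. Withhold the key from pathology until the region-level histology is signed.
4. In Section 4.4, state that masking applies to the malignant/benign call for every region as well as to tumor type.

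The cost is protocol wording, a labeling instruction and one more key to reconcile at data entry. No extra staff, procedures or patients are needed.
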